#### 1.33 *In situ* DC tumor antigen loading for vaccine therapy

Differences in loading of DC with antigen *in vitro* may induce immune tolerance rather than stimulation. The optimal method for preparation of antigen and antigen loading to DC remains to be identified.  Optimal tumor antigen delivery is one of the most important factors for DC-based immunotherapy success. For that reason, autologous tumor cell lysate, whole tumor cells, and mRNA have been tested as antigen providers for DCs.  Furthermore, allogeneic melanoma cell lysates also constitute a valuable alternative (Table 1).

Route of DC delivery also critically impacts efficacy of DC to stimulate an anti- tumor response. Inconsistent generation of systemic anti-tumor immune responses with intravenous and subcutaneous administration has prompted evaluation of novel delivery approach. Intratumor DC delivery was shown to generate anti-tumor immunity and tumor regression in animal models. Also, clinical trials to date have shown this approach to be safe with promising response

Antigen can be generated *in vivo* using conventional therapies including chemical, radiation or even cryoablation. Recently Kolstad et al reported promising results in FL patients treated with radiation, and intra- tumor injection of rituximab and DC. Direct injection *in vivo* offers two advantages: delivery of mature DCs into a milieu of dying tumor cells, resulting in maximum exposure of tumor cell antigens; and avoidance of the suppressive effects of blood monocytes. This combined approach was found to be feasible and safe in prior studies performed by our group in Lymphoma ([name], et. al., unpublished observations). We will evaluate this method in addition to pembrolizumab treatment to enhance clinical efficacy against melanoma.

[figure not shown]
#### 1.34 Safety considerations from DC therapy

DC vaccine therapy clinical trials in melanoma and other types of have thus far demonstrated no significant adverse events or autoimmunity; DC immunotherapy has been used for many different tumors types where adverse events (such as induced autoimmunity) were monitored. Importantly, very few significant adverse effects of DC vaccination have been reported and DC immunotherapy clinical trials performed to date have shown no evidence of resultant generation of auto-immunity. (Table 1). To date, 15 patients with lymphoma, 19 patients with ovarian cancer, and 30 patients with glioblastoma have been treated with DC therapy at Mayo Clinic without any serious drug related toxicity reported. The most common adverse event reported was injection site pain, more often at the time of cryoablation, that usually resolved within 2 days of treatments.

# 1.4 Rationale for pneumococcal conjugate vaccine (PCV) therapy

PCV (Prevnar®) is approved by the US Food and Drug Administration for vaccination against pneumococcal infections in children and works by activating helper T cells to interact with B cells for antibody production.  Pneumococcal vaccination has been shown to be safe and recommended for cancer patients that will or have undergone chemotherapy. Thus, the use of pneumococcal vaccines presents little if any additional risk to the patient.  The use of these vaccines does allow determination of the state of the immune system and its response to the DC based vaccines. Prevnar has been used in two clinical trials for multiple myeloma patients in this manner. These trials included one with adoptive T cell transfer after stem cell transplant and another with lenalidomide.  Both trials reported minimal toxicity. In addition there may be a bystander effect on immunity with enhanced lymphocyte trafficking and the response to one antigen leading to enhanced response to anti-tumor antigens. 

Preliminary studies performed by Yin and colleagues showed that Prevnar13 enhanced mature DC stimulated CD4 T cell proliferation by approximately 1.75 fold compared to mature DC stimulation alone (Figure 1). Importantly, a review of the results of DC therapy in melanoma suggests that addition of adjuvant capable of T cell help significantly improved overall clinical response.  This vaccine will allow us to monitor the immune response prior to and after our intervention. The vaccine will also allow us to quantify any potential in vivo bystander effect due to the combination of DC and pneumococcal vaccine. In the LS1081 study (Vaccine Therapy With or Without Cryosurgery in Treating Patients With Residual, Relapsed, or Refractory B-Cell Non-Hodgkin Lymphoma) no adverse events were seen with Prevnar administrations.

**Figure 1. CD4+ T cell proliferation is stimulated with mature dendritic cells pulsed with Prevnar.** Monocyte-depleted PBMNC from healthy donors were labeled with CFSE and cultured for 7 days without stimulation or with Prevnar, autologous mature dendritic cells (mDC), or autologous mDC pulsed with Prevnar. At the end of culture, cells were stained with 7-AAD, anti-CD3 and anti-CD4 and analyzed by flow cytometry. Percent of live, CD4 T cells that proliferated are shown here for 3 donors. CD4 T cell proliferation was the greatest in co-culture with Prevnar-pulsed mDC.

1.41 Safety considerations for the use of 13-valent pneumococcal conjugate vaccine (PCV) therapy

PCV (Prevnar®) is approved by the US Food and Drug Administration for vaccination against pneumococcal infections in children and works by activating helper T cells to interact with B cells for antibody production. Pneumococcal vaccination is considered safe for cancer patients undergoing chemotherapy with mild side effects including soreness, low-grade fever and induration at the site of vaccination lasting 1-3 days. It has been used in two clinical trials for multiple myeloma patients, one with adoptive T cell transfer after stem cell transplant  and another with lenalidomide. Both trials reported minimal toxicity and some evidence of

improved immune response. As in Rapoport et al, we will use this pneumococcal vaccine to evaluate and monitor the developing immune response. The proposed Prevnar13 (Prevnar) dosing schedule in this study is similar to the Prevnar schedule in LS1081 study. No significant toxicities were observed in 15 patients who received Prevnar along with their DC vaccines. We will use the dose administration and timing as approved for use (Prevnar product insert: http://www.pfizerpro.com/content/showlabeling.asp?id=501).

# **1.5** Cryoablation therapy

# 1.51 Cryoablation background

Percutaneous cryoablation systems are currently available from two manufacturers including HealthTronics, Incorporated (Austin, TX) and Galil Medical (St. Paul, MN); each are FDA 510K cleared for treatment of soft-tissue tumors. Since 2003, investigators in this study have used cryoablation for the treatment of renal, lung, soft tissue, and bone tumors, including treatment of patients enrolled in the LS1081 study. Probes may be placed percutaneously using US or CT image guidance.

The mechanism of cryoablation is based on delivery of argon gas through a segmentally insulated probe with expansion of the gas within the probe lumen, resulting in rapid cooling (via Joule Thompson effect). With expansion of the argon gas within the probe, rapid and extreme temperature drops are produced along the distal, uninsulated probe shaft reaching -100 °C within a few seconds. Adjacent tissues are quickly frozen, resulting in the formation of an iceball. Thawing of the iceball is achieved with either active instillation of helium gas into the cryoprobe instead of argon gas or activation of a small heating element in the distal probe shaft.

Cell death is due to two primary causes. First, rapid freezing immediately adjacent to the probe results in intracellular ice formation, organelle disruption, and subsequent cell destruction. At a further distance from the probe, relative gradual cooling causes osmotic differences across the cell membrane with secondary cellular dehydration and death. Subsequently, further cell death occurs due to thrombosis of affected blood vessels and resultant ischemic necrosis.

The size of the iceball varies depending on the length of uninsulated tip, with commonly used cryoprobes generating an iceball of about 3 cm in diameter and 5 cm in longitudinal length along the probe shaft. The growth and size of the iceball can be controlled by the delivery system through the relative amount of argon passed through the cryoprobe. Importantly, the margins of the iceball are visible with CT, MRI and ultrasound, allowing monitoring of treatment. Given relative cellular tolerance to freezing temperatures, cell death occurs within about 3-5 mm internal to the iceball margin . Following planned cryoprobe placement(s), a target lesion is typically treated with curative intent using two freezing cycles of approximately 10 minutes each, separated by a 5-minute thaw period.

# 1.52 Safety considerations for cryoablation

Outside of the liver, complications due to cryoablation are uncommon. A large experience exists regarding percutaneous cryoablation of renal tumors, showing a major complication rate of 5-8%. . Similar to radiofrequency ablation (RFA), the majority of complications are related to local tissue trauma, including hemorrhage in about 3% of patients. Allowing for a more limited published experience, complications following bone and soft tissue ablation are even more infrequent, ranging from 0- 2% . Unique to cryoablation, compared to RFA, is the ability to visualize the cytotoxic ice develop using CT imaging, allow the user to precisely control the volume of tissue treated and minimize adjacent tissue injury.

Of particular note, a systemic phenomenon called "cryoshock" has been observed primarily in the cryoablation of liver tumors. Cryoshock is clinically manifested by severe coagulopathy, disseminated intravascular coagulation, and multiorgan failure, possibly related to a systemic inflammatory response syndrome. Historically, this syndrome has been seen in about 1% of cases of hepatic cryotherapy and only 0.04% of prostate cryoablations. More recent experience describing percutaneous cryoablation of hepatic tumors in selected patients showed grade 3 or greater complications in 6% of patients, including cryoshock in 3 of 342 procedures (0.9%) (Littrup et al. Abd Rad 2016; 41:767-780). In these 3 patients, tumors measuring larger than 3cm in size were ablated; cryoshock did not occur in the treatment of smaller hepatic lesions.

## 1.6 Rationale for the proposed study and research hypothesis

Among patients with advanced melanoma, pembrolizumab administration is associated with an overall objective response rate of 33%, 12-month progression-free survival rate of 35%, and median overall survival of 23 months;  approximately 25 % of melanoma patients who demonstrated an objective response to pembrolizumab therapy developed disease progression; results are similar to those reported for nivolumab. Moreover, many patients' tumors primarily fail to respond to pembrolizumab.

Agents capable of stimulating infiltration and functional activation of both T cells and APCs in such tumors could synergize with PD-1 blockade to increase the frequency of responding patients and expand the range of tumors treatable with PD-1 inhibitors. Such stimulatory agents have the potential to enhance the extent or durability of responses even in patients who have failed to respond to pembrolizumab monotherapy.

Pembrolizumab (MK-3475) is a highly selective, humanized monoclonal IgG4- $\kappa$  isotype antibody against PD-1 that is approved around the world for the treatment of patients with unresectable or metastatic melanoma with disease progression following ipilimumab and, if BRAFV600 (NCBI accession number NM\_004324.2) mutated, a BRAF inhibitor. Pembrolizumab is well-tolerated at 200mg/3 weeks with an acceptable adverse effects profile. This therapy in combination with an anti-melanoma vaccine capable of expanding melanoma-specific T cells might dramatically improve response rated to Anti-PD-1 therapy.

We will conduct a Phase II clinical trial with a safety run-in phase for patients with unresectable or metastatic melanoma to test the hypothesis that PD-1 blockade combined with cryotherapy and a DC vaccine will have an acceptable adverse event profile and will enhance mDC priming of T cells with anti-tumor antigen and activate T cell functions. Combined immunotherapy with pembrolizumab and cryoablation followed by intra-tumoral injection of mDCs will generate anti-tumor immunity and clinical regression of melanoma in patients who have not responded optimally to PD-1 axis-targeting therapy.

# 2.0 Goals

# 2.1 Primary

To determine the objective response rate (ORR) of pembrolizumab combined with cryoablation and intratumoral mDCs in patients with metastatic melanoma that has failed to respond or has stopped responding to initial therapy with a PD-1 axis-blocking monoclonal antibody.

# 2.2 Secondary

- 2.21 To assess the safety profile of pembrolizumab combined with cryoablation and intratumoral mDCs in patients with metastatic melanoma that have failed to respond or have stopped responding to initial therapy with a PD-1 axisblocking monoclonal antibody.
- 2.22 To determine median progression-free survival (PFS) obtained with this approach in this patient population.
- 2.23 To determine median overall survival (OS) obtained with this approach in this patient population.

# 2.3 Translational

- 2.31 To quantitate tumor infiltrating lymphocytes (TILs) in tumor biopsies prior to and following cryoablation and intratumoral mDCs.
- 2.32 To measure PD-L1 levels in tumor biopsies and blood biopsies prior to and following cryoablation and to assess whether a change in PD-L1 levels differ among those patients who met the criteria for clinical benefit (progression-free and on study for at least 6 months) and those who do not.
- 2.33 To measure peripheral blood mononuclear cells (PBMC) proliferation and function after coculture with frozen tumor before and after intratumoral mDC injection.

# 3.0 Patient Eligibility

## 3.1 Inclusion Criteria

- 3.11 Age  $\geq 18$  years of age on the day of registration.
- 3.12 Histological or cytologically confirmed diagnosis of unresectable stage III or metastatic melanoma (stage IV) not amenable to curative local therapy.
- 3.13 Lack of response to therapy with a PD-1- or PD-L1-targeting monoclonal antibody (pembrolizumab, nivolumab, etc.) after at least 18 weeks of therapy OR documented progression of disease at any time after initiation of therapy with a PD-1- or PD-L1-targeting monoclonal antibody. NOTE: This treatment could have been at any time prior to registration. If given in the adjuvant setting, progression must have been ≤26 weeks after the last dose of therapy.
- 3.14 ECOG Performance Status (PS) 0 or 1 (Appendix I)
- 3.15 Minimum of 3 radiographically apparent lesions such that there is:
  - (1) Minimum of one lesion in areas that have not been previously irradiated that is considered measurable by RECIST 1.1 criteria

AND

(2) Minimum of two lesions in areas that have not been previously irradiated that are determined by Interventional Radiology to be of a size and in a location that a single probe could ablate at least 75% of the lesion.

Note: Hepatic lesions measuring ≤3cm may be treated, as determined by Interventional Radiology.

Note: Brain metastases are not acceptable as lesions defining measurable disease, nor are they candidate lesions for cryoablation.

- 3.16 Adequate venous access for apheresis as assessed by apheresis team. NOTE: If a central venous catheter is required for apheresis, the patient is not eligible.
- 3.17 The following laboratory values obtained  $\leq 14$  days prior to registration.
  - Absolute neutrophil count (ANC)  $\geq 1000/\text{mm}^3$
  - Absolute lymphocyte count  $\geq$  500/mm^3
  - Platelet count  $\geq 100,000/\text{mm}^3$
  - Hemoglobin  $\geq 10 \text{ g/dL}$
  - Total bilirubin ≤1.5 x upper limit of normal (ULN), unless due to Gilbert's disease
  - Aspartate transaminase (AST/SGOT) and alanine transaminase (ALT/SGPT) ≤2.5 x ULN
  - Creatinine  $\leq 1.5$  x ULN or calculated creatinine clearance  $\geq 60$  mL/min for subject with creatinine>1.5 x institutional ULN
- 3.18 Negative serum pregnancy test for persons of childbearing potential  $\leq$ 7 days prior to registration.
- 3.19a Provide written informed consent.
- 3.19b Willing to return to the enrolling institution for follow-up (during active

treatment and active monitoring phase of the study).

14

- 3.19c Willing to provide tissue and blood samples for research purposes (see Sections 6.0, 14.0 and 17.0).
- 3.19d Willing to use adequate contraception while on the study and until 120 days after the last dose of study drug.

#### 3.2 Exclusion Criteria

- 3.21 Choroidal melanoma.
- 3.22 Any of the following because this study involves an investigational agent whose genotoxic, mutagenic and teratogenic effects on the developing fetus and newborn are unknown:
  - Pregnant persons
  - Nursing persons
- 3.23 History of HIV, hepatitis B, or hepatitis C,
- 3.24 Active tuberculosis or active, non-infectious pneumonitis
- 3.25 Evidence of interstitial lung disease
- 3.26 Active infection requiring the use of systemic antibiotics
- 3.27 Symptomatic congestive heart failure (New York Heart Association Classification III or IV cardiovascular disease (Appendix II)), myocardial infarction ≤6 months prior to registration , unstable angina pectoris or cardiac arrhythmia ≤3 months prior to registration, or cardiac arrhythmia.
- 3.28 Currently receiving or have received any other investigational agent considered as a treatment for the primary neoplasm ≤21 days prior to registration.
- 3.29a History of other primary malignancy requiring systemic treatment ≤3 years prior to registration. Patients must not be receiving chemotherapy or immunotherapy for another cancer. Patients must not have another active malignancy requiring active treatment. EXCEPTIONS: Non-melanotic skin cancer or carcinoma-in-situ of the cervix.
- 3.29b Failure to recover from prior side effects of immune checkpoint inhibitor therapy to ≤Grade 1.
   NOTE: Patients will not be excluded for adrenal insufficiency or hypothyroidism secondary to immunotherapy provided they are receiving hormonal replacement
- 3.29c Major surgery  $\leq 4$  weeks prior to registration.
- 3.29d Prior chemotherapy, targeted therapy, or radiation therapy ≤2 weeks prior to registration or who has not recovered (i.e. to ≤Grade 1 or baseline) from an adverse event due to the previously administered therapy.
- 3.29e History of hypersensitivity and anaphylactoid reactions to pneumococcal vaccine or any component of the formulation, including diphtheria toxoid.

3.29f Active autoimmune disease such as Crohn's disease, rheumatoid arthritis, Sjögren's disease, systemic lupus erythematosus, or similar conditions requiring systemic treatment within the past 3 months or a documented history of clinically severe autoimmune disease/syndrome difficult to control in the past.

EXCEPTIONS (the following are allowed):

- Vitiligo or resolved childhood asthma/atopy
- Intermittent use of bronchodilators or local steroid injections
- Non-immunosuppressive maintenance treatments in the setting of clinically asymptomatic disease (e.g., sulfasalazine for ulcerative colitis)
- Hypothyroidism stable on hormone replacement,
- Diabetes stable with current management
- History of positive Coombs test but no evidence of hemolysis
- Psoriasis not requiring systemic treatment
- Conditions not expected to recur in the absence of an external trigger
- Secondary adrenal insufficiency from previous hypophysitis, currently on physiologic replacement steroid dosing only.
- 3.29g Coagulopathy, including the use of therapeutic anticoagulants that cannot be discontinued for the cryoablation procedure.
   NOTE: Heparin for line patency without detectable lab abnormalities for coagulation will be allowed.
- 3.29h Corticosteroid use ≤14 days prior to registration. NOTE: Patients must be off systemic corticosteroids for at least 2 weeks prior to registration. This includes oral or IV route of administration. Patients on chronic corticosteroids for adrenal insufficiency or other reasons may enroll if they receive less than 10 mg/day of prednisone (or equivalent). Patients receiving inhaled or intranasal or intra-articular steroids are not excluded.

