## 7.2 Run-in Phase Ib

7.21 Schedule 1 (6 patients):

Cycle 1, Day 1: Apheresis (see Section 7.3) and pembrolizumab 200mg IV

Cycles 2 and 3, Day 1: Pembrolizumab 200mg IV

Cycles 2 and 3, either Day 1 or Day 2: cryoablation, injection of  $30-60 \times 10^6$  mDCs, and injection of 0.5 ml Prevnar13, per Section 7.4

Cycle 4 Day 1 and all subsequent cycles: pembrolizumab 200mg IV

If at most one of the 6 patients enrolled onto Schedule 1 develops a DLT during the first 3 cycles of treatment then Schedule 1 will be carried forward to the continuation phase.

7.22 Schedule -1:

If two or more patients enrolled onto Schedule 1 develop a DLT during the first 3 cycles of treatment, then an additional 6 patients will be treated as follows:

Cycle 1, Day 1: Apheresis and pembrolizumab 200mg IV

Cycles 2 and 3, either Day 1 or Day 2: Cryoablation, injection of  $30-60 \times 10^6$  mDCs, and injection of 0.5 ml Prevnar13, per Section 7.5. Note: No pembrolizumab will be given in Cycles 2 and 3 on this schedule.

Note: No pembrolizumab will be given in Cycles 2 and 3 on this schedul

Cycle 4 Day 1 and all subsequent cycles: pembrolizumab 200mg IV

- If at most one of the 6 patients enrolled onto Schedule -1 develops a DLT during the first 3 cycles of treatment then Schedule -1 will be carried forward to the continuation phase.
- If two or more of the patients enrolled onto Schedule -1 develop a DLT during the first 3 cycles of treatment, enrollment will be discontinued for the study team to review the safety data and consider amending the protocol.

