# 8.0 Dosage Modification Based on Adverse Events

# 8.1 Treatment schedule modifications in patients based on adverse events

Patients will be evaluated by the study team prior to each dose of pembrolizumab for an adverse event check. Determination will be made if the adverse event is treatment-related (possible, probable or definite), i.e. a toxicity (see Section 10; Adverse event monitoring and reporting). If any adverse event has occurred, then the treatment schedule will be modified as in Section 8.2. If an adverse event occurs during Cycle 2 that requires treatment to be held, then omit pembrolizumab for Cycle 3 and resume pembrolizumab with Cycle 4.

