# 8.2 Treatment schedule modifications for pembrolizumab.

Adverse events (both non-serious and serious) associated with pembrolizumab exposure may represent an immunologic etiology. These adverse events may occur shortly after the first dose or several months after the last dose of treatment. Pembrolizumab must be withheld for drug-related toxicities and severe or life-threatening AEs per Table 8.21 below. See Section 9.0 for supportive care guidelines, including use of corticosteroids.

CTCAE System/Organ/Class		a 1	
(SOC)	Adverse Event	Grade	Action
General disorders and administration site conditions	Infusion related reaction	2	Hold all protocol treatment until Grade 0-1 If AE does not resolve to Grade 0-1 within 3 weeks, then permanently discontinue all protocol treatment
		3-4	Permanently discontinue all protocol treatment
Respiratory, thoracic and mediastinal disorders	Pneumonitis	2	Hold all protocol treatment until Grade 0-1 If AE does not resolve to Grade 0-1 within 3 weeks, then permanently discontinue all protocol treatment
		3-4	Permanently discontinue all protocol treatment
Renal and urinary disorders.	Acute kidney injury or Chronic kidney disease	2	Hold all protocol treatment until Grade 0-1 If AE does not resolve to Grade 0-1 within 3 weeks, then permanently discontinue all protocol treatment
		3-4	Permanently discontinue all protocol treatment
	All Other Nonhematologic Events	3	Hold all protocol treatment until Grade 0-1 If AE does not resolve to Grade 0-1 within 3 weeks, then permanently discontinue all protocol treatment
		4	Permanently discontinue all protocol treatment

Table 8.21	Dose Modification Guidelines for Drug-Related Adverse Events
------------	--------------------------------------------------------------

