Grades 3 or 4 Grade 3: Prolonged (i.e., not rapidly responsive to symptomatic medication and/or brief interruption of infusion); recurrence of symptoms following initial improvement; hospitalization indicated for other clinical sequelae (e.g., renal impairment, pulmonary infiltrates) Grade 4: Life-threatening; pressor or ventilatory support indicated	Stop Infusion.         Additional appropriate medical therapy         may include but is not limited to:         IV fluids         Antihistamines         NSAIDS         Acetaminophen         Narcotics         Oxygen         Pressors         Corticosteroids         Epinephrine         Increase monitoring of vital signs as         medically indicated until the subject is         deemed medically stable in the opinion of         the investigator.         Hospitalization may be indicated.	No subsequent dosing

 Table 9.21
 Infusion reaction treatment guidelines

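### Criterion 3.29b asks only whether earlier checkpoint-inhibitor toxicity has recovered, so a patient with a resolved severe event of a kind that Table 8.21 makes a permanent stop can be given pembrolizumab again

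*Combined protocol and SAP*

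**What the plan says.** **Entry.** Section 3.1, criterion 3.13, requires earlier anti-PD-1 or anti-PD-L1 treatment of everyone. One route in is "Lack of response to therapy with a PD-1- or PD-L1-targeting monoclonal antibody (pembrolizumab, nivolumab, etc.) after at least 18 weeks of therapy". The other is documented progression at any point after such treatment began, with no minimum exposure. The earlier treatment may lie at any distance in the past; progression after adjuvant use must fall within 26 weeks of the last dose.

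Section 3.2, criterion 3.29b, is the only exclusion written for toxicity of that earlier treatment: "Failure to recover from prior side effects of immune checkpoint inhibitor therapy to ≤Grade 1". Its note lets in patients with adrenal insufficiency or hypothyroidism who take hormone replacement.

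**On study.** Section 8.1 sets the attribution standard: "Determination will be made if the adverse event is treatment-related (possible, probable or definite), i.e. a toxicity". In Table 8.21 (Section 8.2) the action is to "permanently discontinue all protocol treatment". For Grade 3-4 infusion reaction, Grade 3-4 pneumonitis, Grade 3-4 events in the row "Acute kidney injury or Chronic kidney disease", and Grade 4 events in the row "All Other Nonhematologic Events", this follows from the grade alone. The Grade 2 rows and the other Grade 3 row instead allow a hold and resumption if the event clears within 3 weeks. For a Grade 3-4 infusion reaction to pembrolizumab, Table 9.21 (Section 9.2) adds "No subsequent dosing".

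**First dose.** Section 7.2, Schedule 1, reads "Cycle 1, Day 1: Apheresis (see Section 7.3) and pembrolizumab 200mg IV". Schedule -1 also gives pembrolizumab on that day and drops it only in Cycles 2 and 3.

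**The concern.** The whole population is being re-exposed to a drug class it has already received, so the entry rule on past class toxicity carries more weight than it would in untreated patients. For certain events the plan judges that, once they occur on study, recovery does not justify another dose. The entry rule makes the opposite judgement about the same kind of event under the earlier antibody: recovery is enough. The documents give no reason for the difference.

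What is at stake is patient safety. A patient could be dosed again with the same drug, or another drug of the same class, after a severe reaction. Moving to Schedule -1 would not avoid this, because the first dose is the same.

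**Working it through.** **Step 1. Does another criterion close the gap?** Each candidate criterion is set against a past severe event that was readily controlled and has fully resolved.

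| Criterion | What it tests | Catches the event? |
|---|---|---|
| 3.17 | Current laboratory limits, including creatinine and liver enzymes | No, once values recover |
| 3.24 | Pneumonitis that is active | No |
| 3.25 | Interstitial lung disease | Only if changes remain |
| 3.29d | Recovery from earlier chemotherapy, targeted therapy or radiation | No, again present status |
| 3.29e | Past hypersensitivity to the pneumococcal vaccine or its components | No, does not cover the antibody |
| 3.29f | Active autoimmune disease, or past disease both severe and hard to control | Not if readily controlled; does not reach infusion reactions |
| 3.29h | Recent systemic steroid use, with a low-dose allowance | No, once steroids are stopped |

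Criterion 3.29f is the nearest to a test of history. It sets no grade and does not name checkpoint-inhibitor events. One of its exceptions, for conditions that should not return without an outside trigger, could be read as letting a drug-induced event back in. The gap remains.

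**Step 2. The plan's own figure.** Section 16.2 states 90% power with 33 patients, 12% against 30%, one-sided level 0.10. It reproduces: the smallest rejection cut-off with exact type I error at or below 0.10 is 7 responses, with error 0.093 and power 0.906. Nothing in this depends on 3.29b.

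**Step 3. How many patients?** The documents do not give the share *q* of otherwise eligible candidates with such a history. Section 15.17 puts pneumonitis and colitis at 1-10% each, and infusion reaction, hepatitis and nephritis below 1% each, without a breakdown by grade. I assume *q* between 1% and 5%. The sample sizes (33, at most 39) and the accrual rate (2 per month) come from Section 16.2.

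- Expected number re-exposed = n × q
- Chance of at least one = 1 − (1 − q)^n
- Extra candidates needed if they are excluded = n/(1 − q) − n
- Extra months = extra candidates / 2

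| n | q | Expected | At least one | Extra candidates | Extra months |
|---|---|---|---|---|---|
| 33 | 1% | 0.33 | 28% | 0.33 | 0.17 |
| 33 | 2% | 0.66 | 49% | 0.67 | 0.34 |
| 33 | 5% | 1.65 | 82% | 1.74 | 0.87 |
| 39 | 1% | 0.39 | 32% | 0.39 | 0.20 |
| 39 | 2% | 0.78 | 55% | 0.80 | 0.40 |
| 39 | 5% | 1.95 | 86% | 2.05 | 1.03 |

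Infusion reaction alone is rarer. At an assumed 0.3-1%, 33 × q gives 0.1-0.3 patients and a 9-28% chance of at least one.

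**The case against.** **The tables govern events on study.** A reader might infer that the protocol contradicts itself, or that it forbids PD-1 treatment for good after such an event. The text supports neither. Table 8.21 says what to do when toxicity arises during the combination; it is silent on recovered events under an earlier regimen. Table 9.21 is written for reactions to pembrolizumab, so it bears directly on a past infusion reaction only if the earlier drug was pembrolizumab. For the other events the argument rests on the shared mechanism. This objection stands and limits the point to a mismatch.

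**Prior toxicity was considered.** Criterion 3.29b exists for it, and a 3.29f exception for adrenal insufficiency after hypophysitis suggests that 3.29f was meant to reach immune drug events. Section 9.2 calls for hospital care and 1 g methylprednisolone in Grade 4 colitis or hepatitis, so few such cases would count as readily controlled. An oncologist supervises treatment (6.5), and 15.17 refers to the package insert. All this shrinks the group but does not remove it: a cleared Grade 3 pneumonitis or a past infusion reaction still passes. The suspension rules in 16.13 act only after toxicity has occurred.

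**Copying Table 8.21 into eligibility would exclude too many.** Combining any other Grade 4 nonhematologic event with attribution down to possible would bar resolved laboratory abnormalities. It would also bar patients whose toxicity came from a CTLA-4 antibody given alongside. This is right, and the fix is narrower for that reason. Entry and stopping rules need not match row for row.

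**The share is assumed.** True. The documents do not show that re-exposure is likely, and the chances of at least one case depend wholly on *q*.

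**Conclusion.** The concern holds as a gap in the entry criteria. A candidate whose earlier anti-PD-1 or anti-PD-L1 antibody caused a severe, readily controlled and now resolved event of a kind that would end treatment on study is eligible as written, and would receive pembrolizumab on the first day under either schedule.

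The number is probably small: 0.3-1.7 of 33 patients, or 0.4-2.0 of 39, if 1-5% of candidates have such a history. That range is an assumption.

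A reader might also infer that such patients would distort the run-in decision or the response test. No such effect is shown, and none is claimed. This is a low-cost safety improvement for the sponsor to consider. Confidence is medium: the reading of the criteria is firm, but the frequency is unknown.

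**What to change.** Add a clause to 3.29b along these lines:

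> *or a history of Grade 3-4 infusion-related reaction, pneumonitis or acute kidney injury, or of a Grade 4 immune-mediated nonhematologic event (such as colitis or hepatitis), attributed to an anti-PD-1 or anti-PD-L1 antibody, whatever its current grade.*

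Four boundaries go with it:

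- Keep the note on adrenal insufficiency and hypothyroidism. Extend it to other endocrine events controlled on replacement, including stable diabetes, which 3.29f already accepts.
- Do not exclude for an isolated, resolved laboratory abnormality that was not immune-mediated.
- Do not exclude for an event attributed to a co-administered CTLA-4 antibody rather than to the anti-PD-1 or anti-PD-L1 antibody.
- Leave chronic kidney disease to the renal limits in 3.17.

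The stops in Table 8.21 that depend on failure to resolve within 3 weeks are left out on purpose, since older records may not show how long an event lasted. Tables 8.21 and 9.21, the sample size, the significance level and the power stay as they are. If the sponsor does intend to rechallenge after such events, a sentence saying so with the reason would serve instead.

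The cost is a few otherwise eligible candidates turned away. At the assumed 1-5%, filling 33 places takes 0.3-1.7 more candidates (0.2-0.9 month at 2 per month); filling 39 takes 0.4-2.1 (0.2-1.0 month).
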